## 9.3 Responsibilities for Reporting Serious Adverse Events

The PI will record all serious adverse experiences that occur during the study period in the appropriate source documents and/or AE log as applicable.

## 9.4 Compliance

It is expected that all involved study personnel (Investigators, study coordinators, ancillary site personnel, and study subjects) will be compliant with the study protocol. Should it be determined that the site is non-compliant, reasonable efforts will be made to secure compliance. These efforts/actions shall be documented in writing and maintained within the study administration file at the Sponsor's location.

Should the site continue to remain non-compliant, the study Sponsor may restrict device availability and/or notify the governing IRB. Should efforts to bring the site into compliance fail, the site may be suspended from study participation until the noncompliance is resolved. Federal regulations require the Sponsor to report non-compliance with the study protocol to the appropriate regulatory authorities. Therefore, in the event of an Investigator or site suspension, the governing IRB and other appropriate regulatory authorities shall be notified.

## 9.5 Protocol Deviations

Protocol Deviations (PDs) will be documented on a Protocol Deviation Case Report Form. PDs are reportable to the institution's governing IRB and regulatory agencies during the annual reporting process, unless otherwise directed by the individual governing IRB requirements or as the specific circumstance dictates.

Every attempt shall be made to adhere to the study protocol. However, should an Investigator be required to deviate from the protocol to protect the life or physical well-being of a study subject in an emergent circumstance, such notice shall be given to the study Sponsor as soon as possible, but no more than 5 working days from the date the event occurred. With the exception of an emergent circumstance, prior approval from Sponsor and the appropriate regulatory authorities is required for any change in, or deviation from, the study protocol as such changes may affect the soundness of the investigation or the rights, safety, and welfare of study subjects.

## 9.6. Investigator Reports and Responsibilities

Investigators are responsible for ensuring the investigation is conducted in accordance with the study protocol and applicable Federal regulations (21 CFR, Part 812, Subpart E). Investigators are also responsible for:

- Obtaining IRB approval for study conduct and re-approval as applicable (if more than one Investigator is participating in the study at a site, the Principal Investigator shall be responsible for the IRB approval and re-approvals)
- Obtaining informed consent of study subjects prior to enrollment into the clinical study
- Protecting the subject rights, safety, and welfare
- Maintenance of subject records and confidentiality
- Record retention as defined in Federal regulations 21 CFR, Part 812.140 (a), (d), and (e)
- Management of investigation and study related activities according to the Clinical Investigator Agreement and the Study Research Agreement
- Submission of site-specific study closure report to governing IRB within 3 months of notification from study Sponsor (if more than one Investigator is conducting the study, the Primary Investigator is responsible for submission of the study closure report)
- Return of any unused investigational product to the study Sponsor upon request or at the conclusion of the clinical study

In addition:

- An Investigator shall report to the Sponsor, within 5 working days, a withdrawal of approval by the reviewing IRB of the Investigator's part of an investigation
- If an Investigator uses a device without obtaining informed consent, the Investigator shall report such use to the Sponsor and the reviewing IRB within 5 working days after the use occurs
- An Investigator shall, upon request by a reviewing IRB or regulatory agency official, provide accurate, complete, and current information about any aspect of the investigation

## 9.7. Sponsor Reports and Responsibilities

The study Sponsor is responsible for ensuring the study is conducted in accordance with the study protocol and applicable federal regulations (21 CFR, Part 812, Subpart C). Further, the study Sponsor is responsible for the following:

- Selecting qualified Investigators and providing Investigators with appropriate information for study conduct
- Ensuring review and approval process for governing IRB is obtained
- Training all clinical investigators in the study on how to properly use the Optiflow™ THRIVE
- Appropriate monitoring of the clinical study
- Prompt notification to the appropriate regulatory and all Investigators of UADE
- Record maintenance and retention per Federal regulations (21 CFR, Part 812.140 (b), (d), and (e)

- Submission of final study closure report that details cumulative study experience to the appropriate regulatory authorities, governing IRBs, and Investigators within 6 months of completing the clinical investigation, in addition to fulfilling annual reporting requirements

In addition:

- A Sponsor who conducts an evaluation of an UADE shall report the results of such evaluation to all reviewing IRBs and participating Investigators within 10 working days after the Sponsor first receives notice of the effect. Thereafter, the Sponsor shall submit such additional reports concerning the effect as an IRB request.
- A Sponsor shall notify all reviewing IRBs and participating Investigators of any withdrawal of approval of an investigation or a part of an investigation by a reviewing IRB within 5 working days after receipt of the withdrawal of approval.
- At regular intervals, and at least yearly, a Sponsor shall submit progress reports to all reviewing IRBs. In the case of a significant risk device, a Sponsor shall also submit progress reports to the regulatory authority.
- A Sponsor shall notify all reviewing IRBs of any request that an Investigator return, repair, or otherwise dispose of any units of a device. Such notice shall occur within 30 working days after the request is made and shall state why the request was made.
- In the case of a significant risk device, the Sponsor shall notify the IRB within 30 working days of the completion or termination of the investigation and shall submit a final report to all reviewing IRBs and participating Investigators within 6 months after completion or termination. In the case of a device that is not a significant risk device, the Sponsor shall submit a final report to all reviewing IRB's within 6 months after termination or completion.
- A Sponsor shall submit to the IRB a copy of any report by an Investigator of use of a device without obtaining informed consent, within 5 working days of receipt of notice of such use.
- If an IRB determines that a device is a significant risk device, and the Sponsor had proposed that the IRB consider the device not to be a significant risk device, the Sponsor shall submit to the appropriate regulatory agency a report of the IRB's determination within 5 working days after the Sponsor first learns of the IRB's determination.
- A Sponsor shall, upon request by a reviewing IRB, provide accurate, complete, and current information about any aspect of the investigation.

## 9.8. Study Termination

The Sponsor may terminate the study at any time. If terminated, the Sponsor will promptly notify the Investigator to cease enrollment of subjects. The study will also be terminated when the objectives have been fully met and all of the designated data collected.

## 10. RISK/BENEFIT ASSESSMENT

### 10.1 Potential Risks

In general, subjects will be a part of a study that may potentially affect how anesthetic providers practice and manage difficult airway patients. The potential risks are the same as routine anesthesia care when related to oxygen therapy/administration. No added risk to study subjects other general precaution or risks related anesthesia care.

### 10.2 Protection Against Risks (Risk Minimization)

The data collection will be terminated if an identifiable adverse event happens. The event will be handled and reported according the standard clinical pathway.

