4. Episodes and percentage duration of oxygen desaturation defined by  $\text{SpO}_2 \leq 92\%$  over the entire procedure
5. Episodes of manual airway support, including jaw thrust, or insertion of an artificial airway device
6. Episodes and duration of BIS number  $\geq 61$  during the entire procedure
7. Episodes of patient movement during the procedure
8. The total dose of propofol used during the entire procedure
9. Patient satisfaction after the procedure by post PACU discharge evaluation (see **Appendix B.**)

**Preoperative care:** No active intervention is planned on this phase of care. All procedures will be provided according to routine clinical care and clinical judgment.

**Intraoperative care:** Total intravenous anesthesia (TIVA) will be delivered using an intravenous infusion of propofol according to anesthesiologist clinical judgment. Intraoperative hemodynamic and temperature will be monitored and maintained according to routine clinical care. A BIS monitor measures the depth of anesthesia with reading between 40-60, as satisfactory.

**Postoperative care:** All patients will be monitored in PACU according to routine clinical care. If deemed necessary by the attending anesthesiologist, patients will be transferred to the intensive care unit.

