## 9. SAFETY AND REPORTABLE EVENTS

For study purposes, adverse events will be categorized at the investigative site into 2 groups: Relatable (Expected) Adverse Events (Grade 1-3) or Serious Adverse Events (Grade 4-5). Therefore, any AEs that are not relatable to the devices, themselves, will not be collected for study purposes. However, all non-relatable AEs will be recorded on the anesthesia record. The PI will determine if the event is related to the device or its deployment, or not related to the device or its deployment will assess the causal relationship of each adverse event.

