### 9.1 Adverse Events Definitions

An adverse event (AE) is any undesirable clinical event occurring to the subject during a clinical study, whether or not it is considered related to the investigational product. This includes a change in a subject's condition or laboratory results, which has or could have a deleterious effect on the subject's health or well-being. An Adverse Event that is related to the investigational device may be referred to as an Adverse Device Effect (ADE). If any of the above-mentioned events occurs, the study will be terminated and case will report according to the standard clinical pathway.

An adverse event does not include:

- Medical or surgical procedures; the condition that leads to the procedure is not an adverse event
- Pre-existing disease, conditions, or laboratory abnormalities present at the start of the study that do not worsen in frequency or intensity
- Situations where an untoward medical occurrence has not occurred (e.g., hospitalizations for cosmetic or elective surgery or social/convenience admissions)
- Expected post-operative course

**Unanticipated Adverse Device Effect (UADE):** Any device related adverse event, the nature or severity of which is not consistent with or listed in the applicable product information (e.g., instructions for use, subject informed consent document, subject information brochure [if applicable], promotional literature) or any other unanticipated serious problem associated with a device that relates to the rights, safety, or welfare of subjects.

A serious adverse event (SAE) is defined as any adverse medical experience that results in any of the following outcomes:

- Death;
- Is life threatening;
- Requires inpatient hospitalization or prolongation of existing hospitalization;
- Results in persistent or significant disability/incapacity;

- Requires medical/surgical intervention to prevent permanent impairment or damage

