## 9.2 Reporting of Adverse Events

All adverse events, whether observed by the PI or study coordinator, elicited from or volunteered by the subject, should be documented. Each adverse event will include a brief description of the experience, the date of occurrence, the date of resolution, the duration and type of experience, the severity, the relationship to investigational product (i.e., drug or device), contributing factors, and any action taken with respect to the study drug/device.

Investigators and research coordinators will be instructed that all AE and corresponding relevant information should be recorded on the Adverse Event Form. In addition, the clinical site will be responsible for notifying the Sponsor within 24 hours of any UADE. All relevant information regarding an UADE should be recorded on the Adverse Event Form and reported to Sponsor via Fax within 24 hours of the event. In addition to the event form, copies of adverse device effect related source documents should be forwarded to the Sponsor.

The Principal Investigator is responsible for reporting AEs to the IRB of record in accordance with IRB procedures. The Sponsor is responsible for informing the appropriate regulatory authorities and other Investigators of any UADEs that have occurred.

The device used in the study is standard anesthesia equipment; further, the study is no more than a data collection process via routine anesthesia care, no modification from routine practice added to a study subject. Therefore, other than general precaution and potential risks from corresponding anesthesia care, the study itself does not have added risk to a study subject other than data collection. No additional risk justification needed for the study.

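### Section 10.2 stops data collection at any adverse event, and no section says that ToLDE recording continues after a severe hypoxic one

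*Combined protocol and SAP*

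**What the plan says.** Section 10.2: "The data collection will be terminated if an identifiable adverse event happens". No grade, relatedness test or exemption for the endpoint is attached.

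Section 9.1 sets a broad definition of an adverse event (AE), which "is any undesirable clinical event occurring to the subject during a clinical study, whether or not it is considered related". The list of what is not an AE does not mention intraoperative hypoxia. After introducing device effects, the section adds: "If any of the above-mentioned events occurs, the study will be terminated and case will report according to the standard clinical pathway". It does not say whether this ends the case or the whole trial. Section 9.8, on termination, does not settle it.

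Section 9 says that "any AEs that are not relatable to the devices, themselves, will not be collected for study purposes", although "all non-relatable AEs will be recorded on the anesthesia record". Section 9.2 says: "All adverse events, whether observed by the PI or study coordinator, elicited from or volunteered by the subject, should be documented".

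The Summary Table and sections 6.1 and 7 set the endpoint: ToLDE, in minutes at SpO2 of 92% or less, over 60 minutes from recorded induction, timed by stop-watch. Section 7 also lists, for the entire procedure, "Episodes and percentage duration of oxygen desaturation defined by" SpO2 of 92% or less, and "Episodes of manual airway support, including jaw thrust, or insertion of an artificial airway device".

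Section 8 names unacceptable AEs among the reasons for withdrawal, ends data collection on withdrawal, and sends the collected data to the pathway for destroying confidential health information. Section 4.1 counts withdrawn patients as randomised but not evaluable and does not replace them. Section 6.2 does not say how to analyse a window shorter than 60 minutes.

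**The concern.** If section 10.2 is followed as written, a severe desaturation can be part of the outcome and also the event that ends its measurement. The patients affected would be those with the most hypoxic time.

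Section 1 gives the pilot's purpose as planning future studies, so its main products are the mean difference in ToLDE and its SD. Cutting off or excluding the longest values tends to make the SD too small. It can also shift the mean difference, even when both arms follow the same rule, if episode lengths differ between devices. Sampling error averages out over repeated pilots; this bias does not.

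**Working it through.** **1. The sections side by side.** Section 10.2 stops recording at an AE. Section 7 ends the window at 60 minutes and counts airway-support episodes, including device insertion. Section 6.2 plans a mean number of hypoxemia episodes, and section 2 calls transient desaturation common. Ordinary desaturation must therefore be recorded through. No section says where an ordinary episode ends and an AE begins, or that recording continues past that line. Sections 9 and 9.2 disagree on which AEs the study collects.

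**2. The plan's own figure.** Section 6.1 gives 0.39 units for 50 per group and SD 1.0. For a difference in means, 1.960 × 1.0 × √(2/50) = 0.392, which reproduces it. If truncated patients were excluded, the half-width would be 0.413 at 45 per group and 0.438 at 40. Bias matters more here than lost precision.

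**3. A bound without a model.** A patient stopped at minute 10 leaves 50 minutes unrecorded. In a 50-patient arm this is at most 50/50 = 1.0 min in the mean.

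**4. Main model (all inputs assumed; the documents give none).** 10% of THRIVE and 30% of mask patients desaturate. Their ToLDE is lognormal with median 2 min and log-SD 0.8 or 1.2, capped at 60 min. A share q of those passing 3, 5 or 10 min is stopped there, and the recorded minutes are used as they stand. The true difference (mask minus THRIVE) is 0.55 or 0.81 min and the pooled SD 1.58 or 3.22 min. Ranges are over both log-SDs and all three cuts:

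| q | Fall in difference | Fall in SD | Patients stopped, of 120 |
|---|---|---|---|
| 10% | 0.3-5% | 1-5% | 0.05-0.9 |
| 25% | 0.8-13% | 3-12% | 0.1-2.2 |
| 50% | 1.6-26% | 5-26% | 0.3-4.4 |
| 100% | 3-53% | 11-73% | 0.5-8.8 |

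The largest shift at q = 25% is about 0.13 × 0.81 = 0.11 min, or 0.11/3.22 = 0.03 SD, against the planned half-width of 0.39 SD. At q = 100% it reaches 0.43 min (0.13 SD). With no stopping at all, 20,000 simulated pilots of 50 per arm gave a 95% range for the SD of 0.8-2.7 (true 1.58) or 1.0-6.5 (true 3.22). The SD bias at q = 10-25% is well inside that.

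**5. Direction.** In the main model the difference shrinks. Now let THRIVE episodes have median 6 min and mask 2 min (log-SD 0.8), with the other inputs unchanged. A true difference of 0.00 min becomes 0.02-0.03 at q = 10%, 0.05-0.08 at q = 25% and 0.18-0.31 at q = 100%, in favour of THRIVE. At q = 100% and a 3-min cut, 60 × (0.10 × 0.807 + 0.30 × 0.306) = about 10 patients are stopped.

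**6. Truncate or exclude.** A second assumed model has Poisson episodes (mean 2 for mask, 1 for THRIVE), exponential lengths with mean 1.5 min, and recording stopped at the first episode over 2, 3 or 5 min. The true difference is about 1.46 min. Recorded minutes as they stand give 0.74, 1.05 and 1.35. Excluding the stopped patients gives 0.59, 0.89 and 1.26. Both shrink the difference, by different amounts, so the choice of rule matters.

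**7. Future sample size.** Required n is proportional to SD²/Δ². If Δ is fixed independently of the pilot, the shortfall in the main model is 1 − (truncated SD/true SD)², which is 2-9% at q = 10% and 5-23% at q = 25%. If Δ is the pilot's own difference, it shrinks too. For example, at q = 25%, log-SD 1.2 and a 3-min cut, (1 − 0.121)²/(1 − 0.132)² = 1.026. The net change is then −2.7% to +1.4% at q = 10% and −7.3% to +2.6% at q = 25%. At q = 50-100% a shortfall remains in most scenarios.

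**The case against.** The trigger is inferred: no section calls hypoxia an AE. Section 9 may confine study AEs to device-related ones, and section 2 attributes desaturation to airway obstruction and propofol-related apnea. The termination sentence in section 9.1 directly follows the one on device effects and may refer only to those. The specific text of section 7 points to continued recording. All of this stands, and it makes the trigger rarer. It does not remove it, because severe hypoxia could be judged related to an oxygen-delivery device and no section says that recording then continues.

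A reader might infer that any fall to 92% or below stops the stop-watch, so that the endpoint cannot be measured. Sections 2, 6.2 and 7 do not support that.

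A reader might also infer that the plan has no handling at all. Sections 8 and 4.1 offer one, though it is not tied to section 10.2 and would drop the worst outcomes. The extra 10 patients per group do not answer the point, since section 6.1 justifies them by aborted radiology cases.

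Nor would the loss necessarily be hidden. Sections 9 and 9.2 have AEs documented, and section 11.3 has missing data queried. What is absent is a commitment to report shortened windows by arm. Source documents and an anesthesia record exist, but they are not said to hold continuous SpO2. The case report forms in Appendix A are not in the text reviewed.

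**Conclusion.** The inconsistency is real and its severity is low to moderate. For a severe hypoxic event or its consequence, the documents do not say whether ToLDE recording continues. Both available readings, truncation or exclusion, lose data in a way that depends on the outcome. This tends to understate the SD and can bias the mean difference towards either arm.

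The size cannot be derived from the documents. It is zero if no hypoxic event is called an AE. In the main model with 10-25% of long episodes stopped, it is below the pilot's sampling noise. The larger figures need nearly every long episode to be stopped, which nothing in the documents suggests.

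A conclusion that future trials would be undersized goes too far. The 2-23% shortfall at those shares holds only if the target difference is set independently of the pilot; otherwise the errors largely offset.

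**What to change.** 1. Replace the sentence in section 10.2 with: *SpO2/ToLDE recording continues to the end of the 60-minute window after any adverse event, unless the patient withdraws consent; the event is also reported.*
2. Reconcile sections 4.1, 7, 8, 9, 9.1, 9.2, 9.8 and 10.2 on whether an AE ends recording, the case or the trial. State that desaturation as such is the endpoint and does not end recording. This concerns measurement only; no clinical stopping rule is proposed here.
3. For withdrawals initiated by the investigator, keep the data already collected and analyse the patient in the randomised arm. Amend the unevaluable wording in section 4.1 and the data-handling wording in section 8 to match.
4. In section 6.2, report incomplete windows by arm with reasons. Add a sensitivity analysis of the mean difference with unrecorded minutes set first to none and then to all at SpO2 of 92% or less, as bounds.

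The cost is protocol wording, one analysis paragraph and some extra minutes of recording in a few patients. Care and sample size do not change.

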## 10.3 Potential Benefits to Subjects

Improved oxygen delivery, administration, and oxygenation (potentially). The data collected during the study may improve the airway safety profile for future procedures. As a specific benefit, the high-flow oxygen delivery may provide stenting of the airway during the procedure and therefore supply additional airway support.

## 10.4 Alternatives to Participation

A standard anesthesia care will be delivered to the study subjects; however, no data collection during the procedure.

